| Table 5: | Renal Monitoring Parameters and Actions to Be Taken | 29 |
| Table 6: | Criteria for Elevated Liver Function Test | 29 |

LIST OF ABBREVIATIONS AND DEFINITIONS OF TERMS

| Abbreviation or Specialist Term | Explanation |
|---------------------------------|--|
| 6MWD | 6-minute walk distance |
| 6MWT | 6-minute walk test |
| AE | adverse event |
| ANCOVA | analysis of covariance |
| ATC | anatomical therapeutic chemical |
| CI | confidence interval |
| CTCAE | Common Terminology Criteria for Adverse Events |
| DMD | Duchenne muscular dystrophy |
| DMDSAT | DMD Functional Ability Self-Assessment Tool |
| ECG | electrocardiogram |
| eCRF | electrical case report form |
| EQ-5D | EuroQoL 5-Dimension |
| ET | early termination |
| FVC | forced vital capacity |
| HRQL | health-related quality of life |
| IRT | interactive response technology |
| ITT | intention-to-treat |
| LoA | loss of ambulation |
| MAR | missing at random |
| MedDRA | Medical Dictionary for Regulatory Activities |
| MEP | maximum expiratory pressure |
| MI | multiple imputation |
| MIP | maximum inspiratory pressure |
| mITT | modified intention-to-treat |
| MMRM | mixed model for repeated measures |
| MRI | magnetic resonance imaging |
| NSAA | North Star Ambulatory Assessment |
| PK | plasma pharmacokinetic |
| PROM | Patient-Reported Outcome Measure |
| PT | preferred term |
| PUL | Performance of Upper Limb |
| rNSAA | revised North Star Ambulatory Assessment total score |
| SAP | statistical analysis plan |
| SOC | system organ class |
| TEAE | treatment-emergent adverse event |
| TFT | timed function tests |
| UN | unstructured covariance matrix |
| WHODRUG | World Health Organization Drug Dictionary |

1. OVERVIEW

This statistical analysis plan (SAP) details the statistical methods to be used in the analyses and presentation of the data collected during the **entire study including open-label treatment period** in Study PTC124-GD-041-DMD, also referred to as Study 041. A separate SAP was prepared to describe the statistical methods to be used for the data collected during the **double-blind treatment period** only.

This document is prepared on the basis of the final study protocol version 4.0 (dated 21JUL2020). The reader is referred to the study protocol, the electronic case report form (eCRF), general eCRF completion guidelines, and various data collection instruments employed in the study for details of study design, conduct and data collection.

There will be 2 database locks for this study. The first database lock (soft lock) occurred on 11April2022 when all subjects completed the 72-week double-blind treatment period. The final database lock will occur when all subjects have completed 72-week open-label treatment period.

2. STUDY OVERVIEW

2.1. Study Design

Study 041 is a Phase 3, international, multicenter, randomized, double-blind, placebo-controlled, efficacy and safety study of ataluren in subjects with nonsense mutation Duchenne muscular dystrophy and its open-label extension.

This study will enroll subjects ≥ 5 years old. Subjects who fulfill all inclusion/exclusion criteria will be randomized in a 1:1 ratio to placebo or ataluren.

Treatment will comprise continuous daily administration of double-blind ataluren or placebo for 72 weeks, followed by open-label ataluren for another 72 weeks. Throughout the study, study drug should be taken three times per day – the 1st dose (10 mg/kg) in the morning, the 2nd dose (10 mg/kg) at mid-day, and the 3rd dose (20 mg/kg) in the evening.

Visits will be performed every 12 weeks during the double-blind treatment period and every 24 weeks during the open-label extension. Visit windows are ± 7 days. The Baseline and Week 72 visits consist of 2 consecutive days. Subjects that discontinue from the study early will complete an early termination (ET) visit. All subjects will have a follow-up phone visit 4 weeks (± 7 days) after the last dose of study drug unless the subject transfers to other ataluren long term follow-up studies.

The primary analysis will be targeted on the subset of subjects who are 7 to 16 years old with 6-minute walk distance (6MWD) ≥ 300 meters and time to stand from supine ≥ 5 seconds at baseline. In subjects who are 5 and 6 years old, a treatment benefit may be obscured due to the confounding effect of normal growth and development. Therefore, subjects who are 5 and 6 years old are eligible for the study but will not be included in the primary analysis. Subjects who are ≥ 17 years old and ambulatory at baseline may be considered to have a milder phenotype and a slower trajectory of disease progression. To limit the variability of study results, these subjects will not be included in the primary analysis population.

2.2. Study Objectives

2.2.1. Primary Objective

The primary objective of this study is to determine the effect of ataluren on ambulation and endurance as assessed by the 6-minute walk test (6MWT).

2.2.2. Secondary Objectives

The secondary objectives of this study are to:

- Determine the effects of ataluren on ambulation and burst activity as assessed by timed function tests (TFT)
- Determine the effects of ataluren on lower-limb muscle function as assessed by the North Star Ambulatory Assessment (NSAA)
- Assess the safety profile of ataluren
- Evaluate the correlation between plasma concentration of ataluren and functional outcomes

- Evaluate the plasma pharmacokinetic (PK) profile of ataluren

2.2.3. Exploratory Objectives

The exploratory objectives of this study are to:

- Determine the effects of ataluren on upper-limb muscle function strength as assessed by the Performance of Upper Limb (PUL) and by the DMD Upper Limb PROM (in subjects ≥ 7 years old at baseline)
- Determine the effects of ataluren on muscle strength as assessed by myometry (in subjects < 7 years old at baseline)
- Determine the effects of ataluren on skeletal muscle integrity as assessed by magnetic resonance imaging (MRI) (at pre-qualified sites only)
- Determine the effects of ataluren on subject- and parent/caregiver-reported health-related quality of life (HRQL) as assessed by at-home questionnaire
- Determine the effects of ataluren on pulmonary function as assessed by forced vital capacity (FVC)

2.3. Study Endpoints for Open-Label Treatment Period

The primary and key secondary efficacy endpoints of this study focus on the comparison of ataluren versus placebo in the double-blind treatment period (baseline to Week 72). These endpoints are described in the SAP for the double-blind treatment period.

The efficacy endpoints below focus on the comparison of subjects receiving ataluren from randomization to Week 144 (hereafter will be referred to as early-start ataluren or ataluren/ataluren) versus subjects receiving placebo from randomization to Week 72 and ataluren from Week 72 to Week 144 (hereafter will be referred to as delayed-start ataluren or placebo/ataluren) across the double-blind and open-label treatment periods.

2.3.1. Primary Endpoint

Not applicable for open-label treatment period

2.3.2. Secondary Endpoints

The following endpoints are considered as secondary endpoints for this study:

- Change from baseline to Week 144 in 6MWD
- Composite of average change in times to run/walk 10 meters, climb 4 stairs, and descend 4 stairs at Week 144
- Change from baseline to Week 144 in time to run/walk 10 meters
- Change from baseline to Week 144 in time to climb 4 stairs
- Change from baseline to Week 144 in time to descend 4 stairs
- Change from baseline to Week 144 in NSAA total score
- Time to loss of ambulation over 144 weeks

- Time to loss of stair-climbing over 144 weeks
- Time to loss of stair-descending over 144 weeks
- Risk of loss of NSAA items over 144 weeks
- Ataluren safety profile characterized by type, frequency, severity, and relationship to study drug of any AEs, or of abnormalities of laboratory tests, vital signs, physical examinations, or ECGs
- Plasma PK at pre-morning dose and 2 hours post-morning dose at Week 144

2.3.3. Exploratory Endpoints

The following endpoints are considered as exploratory endpoints:

- Changes from baseline to Week 144 in PUL total score and domain subscores (in subjects ≥ 7 years old at baseline)
- Change from baseline to Week 144 in DMD Upper Limb PROM total score (in subjects ≥ 7 years old at baseline)
- Risk of loss of DMD Upper Limb PROM items over 144 weeks (in subjects ≥ 7 years old at baseline)
- Change from baseline to Week 144 in myometry parameters (in subjects < 7 years old at baseline)
- Change from baseline to Week 144 in muscle fat fraction as assessed by MRI (at pre-qualified sites only)
- Changes from baseline to Week 144 in HRQL as assessed by EQ-5D
- Change from baseline to Week 144 in FVC

2.3.4. Sample Size

Not applicable for open-label treatment period.

2.4. Randomization

Not applicable for open-label treatment period.

2.5. Blinding

Not applicable for open-label treatment period.

2.6. Study Assessments

2.6.1. 6-Minute Walk Test

The 6MWT will be performed at Screening (Visit 1), baseline (Visit 2, two 6MWTs performed), Week 12 (Visit 3), Week 24 (Visit 4), Week 36 (Visit 5), Week 48 (Visit 6), Week 60 (Visit 7), and Week 72 (Visit 8, two 6MWTs performed), Week 96 (Visit 9), Week 120 (Visit 10), and Week 144 (Visit 11 - End of Treatment/Premature Discontinuation).

2.6.2. Timed Function Tests

Timed function tests of peak physical capacity, including the times taken to run/walk 10 meters, climb 4 stairs, descend 4 stairs, and stand from supine, will be performed using standardized procedures. These assessments will be performed at Screening (Visit 1), baseline (Visit 2), Week 12 (Visit 3), Week 24 (Visit 4), Week 36 (Visit 5), Week 48 (Visit 6), Week 60 (Visit 7), and Week 72 (Visit 8), Week 96 (Visit 9), Week 120 (Visit 10), and Week 144 (Visit 11 - End of Treatment/Premature Discontinuation).

The time taken to stand from supine will not be used as an endpoint in this study.

2.6.3. North Star Ambulatory Assessment

The NSAA measures change in physical function by using standardized procedures and consists of 17 activities, each scored as 0, 1, or 2. The NSAA will be used to evaluate physical function, using standardized procedures. The NSAA will be performed at Screening (Visit 1), baseline (Visit 2), Week 12 (Visit 3), Week 24 (Visit 4), Week 36 (Visit 5), Week 48 (Visit 6), Week 60 (Visit 7), and Week 72 (Visit 8), Week 96 (Visit 9), Week 120 (Visit 10), and Week 144 (Visit 11 - End of Treatment/Premature Discontinuation).

2.6.4. Myometry

Myometry will be performed only in subjects who are <7 years old at baseline.

Upper and lower extremity myometry will be performed using a myometer following standardized procedures. Muscle groups to be evaluated include knee extensors and elbow flexors. Bilateral assessments should be done, and 3 measurements should be recorded from each muscle group on each side if possible. These parameters will be monitored at baseline (Visit 2), Week 12 (Visit 3), Week 24 (Visit 4), Week 36 (Visit 5), Week 48 (Visit 6), Week 60 (Visit 7), and Week 72 (Visit 8), Week 96 (Visit 9), Week 120 (Visit 10), and Week 144 (Visit 11 - End of Treatment/Premature Discontinuation).

2.6.5. PUL and DMD Upper Limb PROM

Both PUL (version 2.0) and DMD Upper Limb PROM will be assessed only in subjects who are ≥ 7 years old at baseline.

PUL is assessed using standard equipment and procedures. The DMD Upper Limb PROM questionnaire will be available in all languages relevant for this study and will be completed by the parent/caregiver. If possible, the same parent/caregiver should complete the questionnaire each time. Both assessments will be performed at baseline (Visit 2), Week 12 (Visit 3), Week 24 (Visit 4), Week 36 (Visit 5), Week 48 (Visit 6), Week 60 (Visit 7), and Week 72 (Visit 8), Week 96 (Visit 9), Week 120 (Visit 10), and Week 144 (Visit 11 - End of Treatment/Premature Discontinuation).

2.6.6. Magnetic Resonance Imaging

MRI and/or magnetic resonance spectroscopy (MRS) will be conducted at a subset of sites that have been qualified by a central imaging vendor to perform this assessment. MRI/MRS data will be analyzed centrally. MRI/MRS will be performed at baseline (Visit 2), Week 24 (Visit 4), Week 48 (Visit 6), and Week 72 (Visit 8), and Week 144 (Visit 11 – End of

Treatment/Premature Discontinuation). The baseline imaging may be performed during the screening period, and post-baseline imaging may be performed ± 4 weeks of visit date.

2.6.7. Spirometry

Spirometric evaluation of FVC and other parameters (eg, maximal inspiratory and expiratory pressures, peak expiratory flow) in the sitting position will be performed at screening (Visit 1), Baseline (Visit 2), and Week 72 (Visit 8), and Week 144 (Visit 11 – End of Treatment/Premature Discontinuation). If a patient loses ambulation as determined by inability to perform the 10-meter run/walk test within 30 seconds at a clinic visit, then spirometry will be performed at that visit and at all subsequent visits.

2.6.8. HRQL At-Home Questionnaires

HRQL will be measured via the EQ-5D and patient-reported functional ability will be measured using the DMD Self-Assessment Tool (DMDSAT).

These questionnaires will only be completed where validated versions in the local language are available and will be completed by the subject (where possible) and a parent/caregiver. If possible, the same parent/caregiver should complete the questionnaire each time. The questionnaires will be provided at Visit 1 and completed at home by the subject and a parent/caregiver between Visit 1 and Visit 2 (pre-treatment) and approximately once per month for the rest of the study. Site personnel will assess subject compliance with the questionnaires will be checked at baseline (Visit 2), Week 12 (Visit 3) Week 24 (Visit 4), Week 36 (Visit 5), Week 48 (Visit 6), Week 60 (Visit 7), and Week 72 (Visit 8), Week 96 (Visit 9), Week 120 (Visit 10), and Week 144 (Visit 11 - End of Treatment/Premature Discontinuation).

2.6.9. Pharmacokinetic (PK) Assessments

Ataluren concentrations in PK samples will be determined using a validated LC-MS/MS method. PK samples at pre-morning dose and 2 hours post-morning dose at Week 144 will be collected.

2.6.10. Adverse Events

An Adverse Event (AE) is any untoward medical occurrence associated with the use of a drug in humans, whether or not it is considered related to the drug.

All AEs (both serious and nonserious) that occur in subjects during the AE reporting period must be recorded. All AEs are to be recorded in the source documents and on the eCRF using concise medical terminology; whenever possible terms contained in Medical Dictionary for Regulatory Activities (MedDRA) should be employed.

2.6.11. Laboratory Assessment

Hematology, biochemistry, and urinalysis laboratory assessment will be analyzed by the central laboratory. These parameters will be measured at Screening (Visit 1), baseline (Visit 2), Week 24 (Visit 4), Week 48 (Visit 6), and Week 72 (Visit 8), Week 96 (Visit 9), Week 120 (Visit 10), and Week 144 (Visit 11 - End of Treatment/Premature Discontinuation).

2.6.12. Vital Signs, Height, Weight, and Physical Examination

Vital signs (including systolic and diastolic blood pressure, pulse rate, and body temperature), height, and weight will be monitored at Screening (Visit 1), baseline (Visit 2), Week 12 (Visit 3), Week 24 (Visit 4), Week 36 (Visit 5), Week 48 (Visit 6), Week 60 (Visit 7), and Week 72 (Visit 8), Week 96 (Visit 9), Week 120 (Visit 10), and Week 144 (Visit 11 - End of Treatment/Premature Discontinuation).

A full physical examination (including evaluation of cardiovascular system, chest and lungs, thyroid, abdomen, nervous system, skin and mucosae, musculoskeletal system, eyes, ears, nose, mouth, throat, spine, lymph nodes, extremities, and genitourinary) will be conducted at Screening (Visit 1), Week 72 (Visit 8) and Week 144 (Visit 11 - End of Treatment/Premature Discontinuation).

A symptom-directed physical examination will be conducted at Baseline (Visit 2), Week 24 (Visit 4), and Week 48 (Visit 6).

2.6.13. 12-Lead Electrocardiogram (ECG)

A 12-lead electrocardiogram (ECG) will be obtained at Screening (Visit 1), Week 24 (Visit 4), Week 48 (Visit 6), Week 72 (Visit 8) and Week 144 (Visit 11 - End of Treatment/Premature Discontinuation). The ECG will be performed and interpreted locally. The findings will be captured with the eCRF.

2.6.14. Echocardiogram

Echocardiogram will be obtained at Screening (Visit 1), Week 72 (Visit 8) and Week 144 (Visit 11 - End of Treatment/Premature Discontinuation).

3. STUDY POPULATIONS

The following study populations will be used to summarize open-label assessments. Refer to double-blind treatment period SAP for other study populations applicable to the double-blind treatment data analyses.

3.1. Intention-to-Treat Population

The intention-to-treat (ITT) population defined in the double-blind treatment period SAP will be used for summary and analysis of open-label efficacy endpoints.

3.2. As-Treated Population for On-Ataluren Analysis

The as-treated population for open-label analysis (hereafter referred to as as-treated-OA) consists of all randomized subjects who receive at least 1 dose of ataluren anytime during the study. This population will be used for summary and analysis of open-label safety endpoints.

4. GENERAL CONSIDERATIONS

4.1. Definitions of Treatment Periods

In general, the open-label data analyses will be based on two treatment periods, the overall treatment period and the on-ataluren treatment period.

Overall treatment period: defined as the period from randomization to the end of study, will be used for analyzing and summarizing efficacy endpoints.

On-ataluren treatment period: defined as the period from the first dose of ataluren, regardless of double-blind or open-label ataluren, to the end of the study, will be used for summarizing safety endpoints.

The corresponding baseline for each treatment period is defined in Section 4.3. The corresponding analysis windows are defined in Section 4.9.

4.2. Tables, Figures, and Listings

Summary statistics for continuous variables will include n (number of subjects), mean, standard deviation, standard error, 95% confidence interval (CI) on the mean, median, minimum, and maximum. Summary statistics for categorical variables will include N (number of subjects in population), n (number of subjects in category), % (percent of subjects in category). Where applicable, the summary data (mean, standard error) will also be provided in graphical presentation.

By-subject data listings will be created for each eCRF domain sorted by treatment, subject, and associated dates, where applicable.

4.3. Baseline and Endpoint Definitions

Two baselines will be used for open-label data analysis, study baseline and on-ataluren baseline.

The study baseline, defined as the last assessment prior to randomization, will be used for analyzing and summarizing efficacy endpoints. Study baseline 6MWD is defined as the maximum measurement of valid Day 1 and Day 2 6MWD values.

The on-ataluren baseline, defined as the last available measurement prior to the first dose of ataluren, will be used for summarizing safety endpoints.

4.4. Baseline Characteristics and Treatment Group Comparability

Baseline characteristics and treatment group comparability will not be summarized in the open-label treatment period.

4.5. Interim Analyses

There is no interim analysis planned for this study. However, there will be 2 database locks for this study. The first database lock (soft lock) will occur when all subjects completed the double-blind treatment (Week 72). The final database lock will occur when all subjects have completed open-label treatment period.

4.6. Multicenter Studies

Summary statistics will be provided by geographic region (North and Latin America, Europe, and Asia Pacific) and/or country to examine potential region effects for the primary endpoint as needed. No statistical tests will be conducted.

4.7. Multiplicity Control

No multiplicity adjustment will be applied to open-label analyses.

4.8. Missing Data Handling

The analyses using a mixed model repeated measures (MMRM) model will be performed based on available data assuming the missing assessments are missing at random (MAR). As sensitivity analyses, missing assessments for the primary and key secondary endpoints based on the analysis of covariance (ANCOVA) will be imputed using pattern-mixture multiple imputation (MI) as described in Section 6.

4.9. Analysis Window

Two sets of analysis windows will be assigned in open-label analyses depending on the treatment period.

Analysis visit windows during overall treatment period will be derived as in [Table 1](#) based on days from randomization to the corresponding visit date. The analysis window during the overall treatment period will be used for efficacy analysis or summaries as appropriate.

Table 1: Analysis Window for Overall Treatment Period

| Analysis Visit | Scheduled Visit Number (study day) | Analysis Window (study day) |
|----------------|------------------------------------|---|
| Week 12 | Visit 3 (85) | [43, 126] |
| Week 24 | Visit 4 (169) | [127, 210] |
| Week 36 | Visit 5 (253) | [211, 294] |
| Week 48 | Visit 6 (337) | [295, 378] |
| Week 60 | Visit 7 (421) | [379, 462] |
| Week 72 | Visit 8 (505) | [463, 546] |
| Week 96 | Visit 9 (673) | [547, 756] |
| Week 120 | Visit 10 (841) | [757, 924] |
| Week 144 | Visit 11 (1009) | Any visit occurred on or after 925 days |

Study day is calculated as visit day – randomization date +1.

Analysis window during on-ataluren treatment period will be derived as in [Table 2](#) based on days from first day of ataluren use to the corresponding visit date. The analysis window during the on-ataluren treatment period will be used for summarizing safety assessments as appropriate.

Table 2: Analysis Window for On-Ataluren Treatment Period

| Analysis Visit for Early-start Ataluren | Scheduled Visit Number (On-ataluren Day) | Analysis Window (On-ataluren days) | Analysis Visit for Delayed-start Ataluren | Scheduled Visit Number (On-ataluren Day) | Analysis Window (On-ataluren days) |
|---|--|---|---|--|--|
| OA Week 12 | Visit 3 (85) | [43, 126] | | | |
| OA Week 24 | Visit 4 (169) | [127, 210] | OA Week 24 | Visit 9 (169) | [2, 253] |
| OA Week 36 | Visit 5 (253) | [211, 294] | | | |
| OA Week 48 | Visit 6 (337) | [295, 378] | OA Week 48 | Visit 10 (337) | [254, 421] |
| OA Week 60 | Visit 7 (421) | [379, 462] | | | |
| OA Week 72 | Visit 8 (505) | [463, 546] | OA Week 72 | Visit 11 (505) | Any On Ataluren visit occurred after 422 OA days |
| OA Week 96 | Visit 9 (673) | [547, 756] | | | |
| OA Week 120 | Visit 10 (841) | [757, 924] | | | |
| OA Week 144 | Visit 11 (1009) | Any visit occurred on or after 925 days | | | |

OA = on-ataluren. On-ataluren day is calculated as visit date – first dose of ataluren date + 1.

All assessments will be assigned to a study analysis visit based on the corresponding study days. For a given subject, if multiple assessments are within the same analysis window, the one closest to the scheduled visit day will be used for that analysis visit. In case of equal number of days to the scheduled visit day, the later assessment will be used for that given analysis visit.

For 6MWD at Visit 8, the date corresponding to the maximum of Day 1 and Day 2 will be used for deriving the study analysis visit.

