4.8. Study Analysis Visit

Study analysis visits during double-blind treatment period will be derived as listed in [Table 2](#) based on days from randomization date to the corresponding visit date. Study analysis visits will be used in all by-visit summaries for both efficacy and safety assessments.

Table 2: Study Analysis Visit

| Analysis Visit | Scheduled Visit Number (Study Day) | Analysis Window (Study Day) |
|----------------|------------------------------------|---|
| DB Week 12 | Visit 3 (85) | [43, 126] |
| DB Week 24 | Visit 4 (169) | [127, 210] |
| DB Week 36 | Visit 5 (253) | [211, 294] |
| DB Week 48 | Visit 6 (337) | [295, 378] |
| DB Week 60 | Visit 7 (421) | [379, 462] |
| DB Week 72 | Visit 8 (505) | Any double-blind visit occurred on or after Day 463 |

Abbreviations: DB, double-blind.

Study day is calculated as visit date - randomization date + 1.

All assessments will be assigned to a study analysis visit based on study days. For a given subject, if multiple assessments are within the same analysis window, the one closest to the scheduled study day will be used for that analysis visit. In case of equal number of days to the scheduled visit date, the later assessment will be used for that given analysis visit.

For 6MWD at the Week 72 Visit (Visit 8), the date corresponding to the maximum of Day 1 and Day 2 will be used for deriving the study analysis visit.

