4.10. Addressing the Impact of Coronavirus Disease of 2019 (COVID19)

Study visits have been impacted by site closures and travel restrictions due to Coronavirus Disease of 2019 (COVID19). Mitigation strategies have been implemented to reduce the number of missed or delayed visits for the study, including allowing subjects to have visits outside of the protocol defined window (± 7 days). To minimize the impact from the out-of-window assessments, the actual week, instead of nominal visit, will be used in statistical modelling, where appropriate.

The protocol described MMRM model using actual week at the visit will be considered as primary efficacy analysis method. The protocol proposed the analysis of ANCOVA model analyzing 6MWD at Week 72 after MI assumes that almost all subjects have visits within protocol defined window will be considered as sensitivity analysis.

In addition, to assess the impact of COVID19, a sensitivity analysis for 6MWD using MMRM and ANCOVA after MI after removing all COVID19 impacted visits will be performed for mITT and ITT populations as described in Section [6.1.3.6](#).

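### The open-label SAP ends the Week 72 window at Day 546, so a Visit 8 held 42 or more days late becomes a Week 96 candidate there but falls in the Week 72 window of the double-blind SAP

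*SAP*

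**What the plan says.** Open-label SAP, Section 4.9, Table 1 has adjacent rows "Week 72 | Visit 8 (505) | [463, 546" and "Week 96 | Visit 9 (673) | [547, 756" (both ranges inclusive). The section adds: "The analysis window during the overall treatment period will be used for efficacy analysis or summaries as appropriate". Two rules govern assignment. The first is "All assessments will be assigned to a study analysis visit based on the corresponding study days". The second is "if multiple assessments are within the same analysis window, the one closest to the scheduled visit day will be used for that analysis visit", with ties going to the later assessment. The only provision specific to Visit 8 settles which of its two 6MWT dates is used; nothing refers to treatment phase.

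Double-blind SAP, Section 4.8, Table 2 gives the Week 72 window as "Any double-blind visit occurred on or after Day 463", with no upper limit. The day origin is the same in both plans: "Study day is calculated as visit date - randomization date + 1".

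Double-blind SAP, Section 4.10 says that the COVID-19 mitigation included "allowing subjects to have visits outside of the protocol defined window", and that actual week would be used in modelling to limit the effect. The open-label 6MWD model (open-label SAP, Section 6.2.1) uses analysis visit as a category, so there the windows alone decide each record's time point.

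**The concern.** Visit 8 is the last assessment before crossover: the protocol's schedule of events has open-label drug first dispensed at that visit. If it is held late enough, the open-label SAP can relabel it as the first assessment after crossover. A measured end-of-double-blind 6MWD may then be dropped, or a placebo boy's last untreated value may stand at a time point that the reader takes as 24 weeks on ataluren. The Week 72 results for the same boys would also not reproduce between the double-blind and open-label reports.

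**Working it through.** **Inputs.** Target days from open-label Table 1: 85, 169, 253, 337, 421, 505, 673, 841, 1009, with Day 1 as baseline. The stated lower bounds come from the same table.

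**Step 1: the rule behind the table.** Lower bound = (previous target + own target) / 2.

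| Analysis visit | Midpoint | Stated lower bound |
|---|---|---|
| Week 12 | (1+85)/2 = 43 | 43 |
| Week 24 | (85+169)/2 = 127 | 127 |
| Week 36 | (169+253)/2 = 211 | 211 |
| Week 48 | (253+337)/2 = 295 | 295 |
| Week 60 | (337+421)/2 = 379 | 379 |
| Week 72 | (421+505)/2 = 463 | 463 |
| Week 96 | (505+673)/2 = **589** | **547** |
| Week 120 | (673+841)/2 = 757 | 757 |
| Week 144 | (841+1009)/2 = 925 | 925 |

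Eight of nine match. The exception equals 505 + 42, half of a 12-week interval, although Visit 9 comes 24 weeks after Visit 8. Days 547 to 588 (588 − 547 + 1 = 42 days) are nearer to Day 505 yet are assigned to Week 96.

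**Step 2: how late is late.** Day 547 is 547 − 505 = 42 days after target and 547 − 512 = 35 days beyond the +7-day visit window.

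**Step 3: one assessment under two plans.**

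| Double-blind Visit 8 on | Days from 505 / 673 | Open-label SAP | Double-blind SAP |
|---|---|---|---|
| Day 512 | 7 / 161 | Week 72 | Week 72 |
| Day 546 | 41 / 127 | Week 72 | Week 72 |
| Day 547 | 42 / 126 | Week 96 | Week 72 |
| Day 560 | 55 / 113 | Week 96 | Week 72 |
| Day 588 | 83 / 85 | Week 96 | Week 72 |
| Day 600 | 95 / 73 | Week 96 | Week 72 |

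**Step 4: what happens to the value.**

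- *Visit 8 on Day d from 547 to 588, Visit 9 held 168 days later.* Visit 9 is d − 505 days from Day 673 and Visit 8 is 673 − d days from it, so Visit 9 is closer whenever d < 589. For d = 560, Visit 9 falls on Day 728: 55 against 113 days. Visit 8 is dropped. The same happens if Visit 9 is on schedule at Day 673. With later visits present, Week 72 becomes an intermediate gap, which step 1 of the imputation in Appendix 2 fills.
- *Same Visit 8, no valid later assessment by Day 756.* Visit 8 becomes the Week 96 value.
- *Visit 8 on Day 589, Visit 9 on Day 757.* Visit 8 becomes Week 96 and Visit 9 becomes Week 120. The Visit 9 shift comes from counting days from randomization, not from the 546/547 cut; the Visit 8 label is the part that conflicts with the double-blind SAP.

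**Step 5: a moved cut on its own.** Take Visit 8 on Day 505 and an open-label premature-discontinuation visit on Day 560 (protocol, End of Treatment section). Under the present table the second is Week 96. With Week 72 set to [463, 588], both fall in Week 72, Visit 8 is closer (0 against 55 days), and the boy's open-label value is lost. If his Visit 8 test were invalid, an on-ataluren value would stand as Week 72 for a placebo boy. A moved cut also leaves the two plans in conflict from Day 589 onward.

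**The case against.** The arithmetic is not in dispute; the case against concerns consequence.

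- **The cut may be deliberate.** [463, 546] is the same 84-day window as for the other double-blind visits, and a tight upper bound keeps post-crossover assessments out of Week 72. That aim is sound. But study day is only a proxy for treatment phase, and the table protects in one direction only.
- **Nothing confirmatory depends on it.** The Week 72 endpoints belong to the double-blind SAP, which has its own window. The open-label change endpoints are at Week 144, and no multiplicity control is applied. This stands.
- **Occurrence is not shown.** Out-of-window visits were allowed, but no document says that any Visit 8 was 42 days late. This stands.

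Three stronger readings are tempting, and the documents do not support them. A reader might infer that every such boy loses his Week 72 value. A late Visit 7 in [463, 546] can fill it: with Visit 7 on Day 470 and Visit 8 on Day 560, both plans choose Day 470 (35 against 55 days from target). A reader might infer that unexposed values enter Week 96 in both arms. Ataluren/ataluren boys were assigned drug from randomization, so this applies only to placebo/ataluren, and only when no closer assessment lies in the Week 96 window. A reader might infer that the Week 144 contrast is directly distorted. Weeks 72 and 96 reach it mainly through the covariance structure and the imputation inputs, unless later visits also shift.

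**Conclusion.** The defect is real and limited. The 546/547 boundary departs from the rule that produced the other eight lower bounds, and it conflicts with the double-blind SAP for any double-blind Visit 8 on Day 547 or later. For those boys the open-label analysis either discards the Visit 8 value or analyses it as Week 96. The quantities exposed are the Week 72 and Week 96 levels of the categorical MMRM, the by-visit efficacy summaries and the Week 72 and Week 96 imputation variables. Any Visit 8 within ±7 days is untouched, and the double-blind results are not affected.

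This rests on reading the assignment rule as written, by study day with no unstated exception for treatment phase, and on at least one Visit 8 having been that late. The documents cannot confirm the second. It should be corrected because the rule gives a wrong label whenever it applies and correction is cheap; it is not a threat to the main conclusions.

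**What to change.** Add a two-way treatment-phase rule to open-label SAP Table 1:

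- Any assessment on or after Day 463 and before the first open-label dose maps to Week 72, as in the double-blind SAP.
- Any assessment after the first open-label dose maps to Week 96 or later.
- The day windows and the closest-to-target rule then apply within each phase.

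The text should also say how an assessment dated on the day of that first dose is classed. With this rule, Visit 8 on Day 560 is Week 72 and Visit 9 on Day 728 is Week 96, while the open-label discontinuation visit on Day 560 in step 5 stays at Week 96. The two plans then agree on the window for a late Visit 8 on every day. Do not move the cut to 588/589 without the phase rule.

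The early-start columns of Table 2 repeat [463, 546] and [547, 756]. Use the same mapping there for consistency; those columns serve descriptive safety summaries only.

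Report, by arm, how many Visit 8 assessments fell on or after Day 547, so that readers can see whether the issue arose.

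Cost: a sentence, table notes and a re-derivation of analysis visits. No new data are needed.
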